#### **5.4.2 Discontinuation of Entire Study**

AbbVie may terminate this study prematurely, either in its entirety or at any study site, for reasonable cause provided that written notice is submitted in advance of the intended termination. The investigator may also terminate the study at his/her site for reasonable cause, after providing written notice to AbbVie in advance of the intended termination.

Advance notice is not required by either party if the study is stopped due to safety concerns.

If AbbVie terminates the study for safety reasons, AbbVie will immediately notify the investigator by telephone and subsequently provide written instructions for study termination.

#### **5.4.3 Discontinuation of Subjects Meeting Virologic Failure Criteria**

The following criteria will be considered evidence of virologic failure during the study treatment period. Pediatric subjects demonstrating any of the following should be discontinued from study drug:

- Confirmed increase from nadir (defined as 2 consecutive HCV RNA measurements  $> 1 \log_{10}$  IU/mL above nadir) in HCV RNA at any time point
- Confirmed HCV RNA  $\geq 100$  IU/ml (defined as 2 consecutive HCV RNA measurements  $\geq 100$  IU/ml) at any point after achieving HCV RNA  $<$  LLOQ

Confirmatory testing, where required, should be completed as soon as possible. Also, when confirmation is required, the subject should remain on study treatment until the virologic failure has been confirmed.

If any of the above criteria are met during the study treatment period, the subject should discontinue study treatment but continue in the PT Period. If the investigator believes the virologic failure is due to study drug interruption and/or is compliance related, the AbbVie Study TA SD/TA MD should be contacted to discuss alternative management.

## **5.5 Treatments**

### **5.5.1 Treatments Administered**

Each dose of open-label DAA study drugs (ombitasvir, paritaprevir, ritonavir and dasabuvir) and ribavirin will be dispensed in the form of tablets, mini-tablets, or as an oral solution (RBV only). Study drugs will be dispensed at the visits listed in [Appendix C](#).

#### Adult Formulations:

Ombitasvir/paritaprevir/r will be provided by the Sponsor as 12.5 mg/75 mg/50 mg tablets. Ombitasvir/paritaprevir/r will be taken orally as 2 tablets every morning which corresponds to an ombitasvir 25 mg/paritaprevir 150 mg/ritonavir 100 mg dose QD.

Dasabuvir will be provided by the Sponsor as 250 mg tablets. Dasabuvir will be taken orally as 1 tablet twice daily, which corresponds to a 250 mg dose BID.

#### RBV: Parts 1 and 2

RBV will also be provided to the investigator by the Sponsor for use in this study. RBV will be provided as 200 mg tablets for subjects that are willing to swallow those tablets. For subjects that are not willing to swallow the RBV tablets and not taking the adult formulations of the DAAs, RBV will be provided as a 40 mg/mL oral solution. Management of RBV in renally impaired patients ( $\text{CrCl} < 50 \text{ mL/min}$ ) will be left to the physician's discretion in consultation with the Therapeutic Area Medical Director.

#### Part 1 Mini-Tablet:

Ombitasvir, paritaprevir and ritonavir will be provided by the Sponsor as separate 0.3 mg, 1.0 mg, and 1.0 mg mini-tablets. Ombitasvir, paritaprevir and ritonavir will be taken orally and will be dosed QD based on body weight.

Dasabuvir will be provided by the Sponsor as 3.08 mg mini-tablet. Dasabuvir will be taken orally and will be dosed BID based on body weight.

The mini-tablets are packed in unit doses and are to be administered at once. The legal guardian(s) should be counselled by site to check that the study drug bottles have been emptied completely into the dosing vehicle to assure the complete dose is taken by the subject. Ombitasvir, Paritaprevir, Ritonavir will be taken orally and will be dosed QD based on body weight. Dasabuvir will be taken orally and will be dosed BID based on body weight.

On the morning of Study Day 1, at the site, subjects will be administered study drugs by the study site personnel and receive instructions for self-administration of all study drugs from the Day 1 evening dose of dasabuvir or Study Day 2 through Study Week 12 of the Treatment Period. The date and time of administration of the first dose of each drug will be recorded in the source and eCRF.

Following enrollment, the site will use the IRT system for drug dispensation. Study drugs must not be dispensed without contacting the IRT system, and only for subjects enrolled in the study through the IRT system.

All subjects who receive at least one dose of study drugs who fail to achieve virologic suppression, or who experience virologic breakthrough on DAA therapy will be discontinued from treatment and enter the Post-Treatment Period, unless alternative management is agreed to with AbbVie Study TA SD/TA MD. The investigator can prescribe another regimen, as deemed appropriate, which will not be provided or reimbursed by AbbVie.

### **5.5.2 Identity of Investigational Products**

Information regarding the study drugs to be used in this study is presented in [Table 10](#).

**Table 10. Identity of Investigational Products**

Part	Investigational Product	Manufacturer	Mode of Administration	Formulation	Strength
1 & 2	Ombitasvir/paritaprevir/ ritonavir	AbbVie	Oral	Tablets	12.5/75/50 mg
1 & 2	Dasabuvir	AbbVie	Oral	Tablets	250 mg
1	Ombitasvir	AbbVie	Oral	Mini-tablets	0.3 mg
1	Paritaprevir	AbbVie	Oral	Mini-tablets	1.0 mg
1	Ritonavir	AbbVie	Oral	Mini-tablets	1.0 mg
1	Dasabuvir	AbbVie	Oral	Mini-tablets	3.08 mg
1 & 2	Ribavirin	Kadmon/ AbbVie	Oral	Tablets	200 mg
1	Ribavirin	Merck	Oral	Solution	40 mg/mL
2	Ribavirin	MSD Sharp & Dohme	Oral	Solution	40 mg/mL

### 5.5.2.1 Packaging and Labeling

Part 1: Ombitasvir/paritaprevir/ritonavir tablets, dasabuvir tablets, all mini-tablets, RBV tablets or oral solution will all be provided in bottles. Each bottle will be labeled as required per country requirement. Labels must remain affixed to the bottles.

Part 2: Adult formulation ombitasvir/paritaprevir/ritonavir tablets and dasabuvir tablets will be provided in bottles. Ribavirin tablets and oral solution will be provided in bottles. All products will be labeled as required per country requirement and labels must remain affixed.

All blank spaces (if applicable) on the study drug labels should be completed by site staff prior to dispensing to subjects.

### 5.5.2.2 Storage and Disposition of Study Drugs

All study drugs, with the exception of the ribavirin oral solution, must be stored at controlled room temperature (15° to 25°C/59° to 77°F) according to labeled storage conditions. Ribavirin oral solution should be stored at refrigerated or controlled room temperature (2° to 30°C/36° to 86°F).

Part 1: Ombitasvir 0.3 mg, paritaprevir 1.0 mg, ritonavir 1.0 mg and dasabuvir 3.08 mg mini-tablets will be supplied to the site in bottles.

Mini-tablets can be administered in a dosing vehicle (e.g., applesauce, see dosing card for instructions).

RBV for both Part 1 and 2: RBV tablets and solution will be administered according to the local RBV label and provided by the sponsor to the sites. A dosing syringe for the RBV solution intake will be provided by the sponsor to the sites.

The investigational products are for investigational use only and are to be used only within the context of this study. The study drug supplied for this study must be maintained under adequate security and stored under the conditions specified on the label until dispensed for subject use or returned to the AbbVie. Upon receipt of study drugs, the site will acknowledge receipt within the IRT system.

### **5.5.3 Method of Assigning Subjects to Treatment Groups**

At the Screening Visit, all subjects will be assigned a unique subject number through the use of IRT. For subjects who do not meet the study selection criteria (or who are unable to enroll before enrollment has closed), the site personnel must contact the IRT system and identify the subject as a screen failure.

First, the subjects in the  $\geq 12$  to 17 year age group of Part 1 who are  $\geq 45$  kg and willing to swallow the adult formulations will be enrolled, then sequential enrollment into the other age groups of Part 1 will start (Section 5.1). Enrollment in Part 2 will begin once dosing recommendations of OBV, PTV, RTV and DSV are available for the  $\geq 12$  to 17 year-old age group based on the pharmacokinetic and clinical data from Part 1 of the study (Section 5.1). Subjects who are enrolled will retain their subject number assigned at the Screening Visit throughout the study. For enrollment of eligible subjects into the study, the site will utilize the IRT system in order to receive unique study drug kit numbers according to the regimen assigned (Table 5 and Table 6). In Part 1, the study drug kit numbers will be assigned to daily doses assigned to a site according to schedules

computer-generated before the start of the study by the AbbVie Data and Statistical Sciences Department.

In Part 1 of the study, caps on the number of subjects in each group in IRT will be employed to ensure that approximately 12 subjects in each age group are enrolled.

In Part 2 of the study, caps on GT1 and GT4 subjects will be employed in IRT to ensure that approximately 10 genotype 4-infected subjects regardless of prior treatment experience and cirrhotic status are enrolled.

Contact information and user guidelines for IRT use will be provided to each site.

#### **5.5.4 Selection and Timing of Dose for Each Subject**

Selection of the doses for this study is discussed in Section 5.6.5. The daily dose assigned to each subject in Part 1 will be assigned by IRT according to the formulation used and the weight of the subject. In Part 2, the study drugs will be provided in unit doses and the number of unit doses to be administered per day will be assigned by IRT according to the formulation used (to be determined from Part 1) and the weight of the subject.

Study drug dosing will be initiated at the Study Day 1 Visit. OBV, PTV, RTV will be dosed QD and DSV (if applicable) will be dosed BID. Thus with normal dosing, 1 dose of OBV, PTV, RTV and DSV (if applicable) should be taken in the morning, and 1 dose of DSV should be taken in the evening. RBV (if applicable) will be dosed according to the local label. RBV dose modifications will be assessed by the Investigator following the RBV Dose Modification Guideline (Table 12), taking into account the subject's clinical and safety parameters in conjunction with the Therapeutic Area Medical Director.

All study drugs should be dosed together and administered with food at approximately the same time in the morning every day, i.e., the AM dose of OBV, PTV, RTV, DSV (if applicable) and RBV (if applicable) should be taken together with food and the PM dose of DSV (if applicable) and RBV (if applicable) should be taken together and with food.

### **5.5.5 Blinding**

This is an open-label study.

### **5.5.6 Treatment Compliance**

The investigator or his/her designated and qualified representatives will administer/dispense study drug only to subjects enrolled in the study in accordance with the protocol. The study drug must not be used for reasons other than that described in the protocol.

All study drugs will be dispensed to subjects by study-site personnel under the direction of the investigator. At the start of the study, each subject along with their parent(s)/guardian(s) should receive counseling regarding the importance of dosing adherence with the treatment regimen with regard to virologic response and potential development of resistance. The start and stop dates of all study drugs will be recorded in the source documents and eCRFs. When dosing mini-tablets, the bottles should be checked thoroughly to ensure that no mini-tablets remained inside the bottle.

During the Treatment Period, subjects will be instructed to bring all study drug units (full, partial or empty) to the study site at each study visit. The study site personnel will inspect the contents of the study drug bottles and account for the returned study drug electronically at each Study Drug Accountability visit indicated in [Appendix C](#). If poor adherence is noted, the subject and parent(s)/guardian(s) should be counseled and this should be documented in the subject's source document.

### **5.5.7 Drug Accountability**

The investigator or his/her representative will verify that study drug supplies are received intact and in the correct amounts. This will be documented by signing and dating the Proof of Receipt (POR) or similar document and via recording in the IRT system. A current (running) and accurate inventory of study drug will be kept per subject by the investigator. An overall accountability of the study drug will be performed and verified by the AbbVie monitor throughout the Treatment Period. The monitor will review study

drug accountability on an ongoing basis. Final accountability will be verified by the monitor at the end of study drug treatment at the site.

During the study, should an enrolled subject misplace or damage a study drug unit, the IRT system must be contacted and informed of the misplaced or damaged study drug. If the study drug unit is damaged, the subject will be requested to return the remaining study drug to the site. Replacement study drug may only be dispensed to the subject by contacting the IRT system. Study drug replacement(s) and an explanation of the reason for the misplaced or damaged study drug(s) will be documented within the subject's source. Date of the first dose and the last dose of the regimen will be documented in the subject's source documents and recorded on the appropriate eCRF.

The return status of each study drug unit and the date of reconciliation will be documented at Study Drug Accountability Visits in [Appendix C](#).

Detailed instructions regarding study drug accountability are provided below.

#### Adult Formulations and RBV Tablets Part 1 and Part 2

The number of tablets of each type of study drug returned in each bottle will be noted in the IRT system and on a drug accountability log (if appropriate). Labels must remain affixed to the bottles.

#### Mini-Tablet Formulation (Part 1)

The status of each returned mini-tablet bottle will be noted in the IRT system and on a drug accountability log (if appropriate). The Investigator/designee must document the status of the returned bottles as full/sealed or empty or unsealed but not empty in the IRT system. Labels must remain affixed to the bottles.

#### RBV Solution Part 1

The status of each returned RBV solution bottle will be noted in the IRT system and on a drug accountability log (if appropriate). The Investigator/designee must document the

status of the returned RBV solution bottle as full/sealed or empty or unsealed but not empty in the IRT system. Labels must remain affixed to the bottles. Supporting drug accountability data will be transcribed by the Investigator/designee from the RBV solution diary into the EDC system.

Upon completion of or discontinuation from the Treatment Period, all original study drug units (containing unused study drugs) will be returned to the Sponsor (or designee) or destroyed on site. All destruction procedures will be according to instructions from the Sponsor and according to local regulations following completion of drug accountability procedures. All empty original study drug units shall be disposed of onsite following completion of study drug accountability and reconciliation procedures. Labels must remain attached to the study drug units.

## **5.6 Discussion and Justification of Study Design**

### **5.6.1 Discussion of Study Design and Choice of Control Groups**

The combination regimen of OBV, PTV, RTV, with DSV (GT1) or without DSV (GT4) and with RBV (GT1a and GT4) or without RBV (GT1b) for 12 or 24 weeks (GT1a cirrhotic subjects only) is currently approved in adults in several countries including the US and in the EU. The dose, durations, and regimens have been optimized for a given HCV genotype/sub-genotype and cirrhosis/non-cirrhosis status in adults. These same durations and regimens are anticipated to be similarly successful in children as long as the drug exposures are comparable, so further regimen/duration exploration is not warranted. In addition, no interferon-free regimens are approved for use in children; the approved standard of care (pegIFN/RBV) has notably lower efficacy rates and a worse safety profile than the interferon-free DAA regimens and requires a longer treatment duration, making a comparative study unethical and difficult to enroll. A non-randomized parallel study design with regimens/duration and drug exposure comparable to the recommended adult regimens is the best method for evaluation.

## **5.6.2 Appropriateness of Measurements**

Standard pharmacokinetic, statistical, clinical, and laboratory procedures will be utilized in this study. HCV RNA assays are standard and validated. The EQ-5D-3L instrument is standard in the literature and thoroughly validated in studies of the pediatric population and in pediatric subjects who have chronic health conditions.

## **5.6.3 Justification of Primary and Secondary Endpoint Success Criteria**

According to the Highlights of Prescribing Information of PEGASYS®, the SVR24 rate was 47% among 45 treatment-naïve pediatric subjects with HCV GT1 in the NV17424 trial. To show that the DAA regimen is superior to this current standard of care by 20%, the lower bound of the 2-sided 95% confidence interval of the SVR12 rate across all subjects in the study must be greater than 67%.

For the secondary endpoints of the percentage of subjects with SVR12 by formulation, age and weight group, the percentage of subjects with SVR24, and the percentage of subjects with ALT normalization during treatment, the simple percentage will be calculated along with a 2-sided 95% confidence interval. The lower bound of the 2-sided 95% confidence interval of the SVR24 rate across all subjects in the study will also be compared to 67%. ALT normalization is defined as the percentage of subjects with ALT at or below the upper limit of normal (ULN) at the final treatment visit among subjects with ALT > ULN at baseline, and will be presented along with a 2-sided 95% confidence interval.

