In Part 2, the primary objectives are to further evaluate the safety and efficacy (percentage of treatment-naïve or treatment-experienced subjects achieving  $SVR_{12}$ ) of OBV/PTV/RTV and DSV with or without RBV in HCV GT1-infected pediatric subjects and OBV/PTV/RTV in GT4-infected pediatric subjects with or without compensated cirrhosis. Part 2 will enroll approximately 16 HCV GT1-infected and 10 GT4-infected, treatment-naïve or IFN (IFN or pegIFN with or without RBV) treatment-experienced pediatric subjects ages  $\geq 12$  to 17 years of age. Enrollment in Part 2 will begin once dosing recommendations of OBV, PTV, RTV and DSV are available for the  $\geq 12$  to 17 year-old age group based on the pharmacokinetic and clinical data from Part 1 of the study. Subjects who take at least one dose of the study drug will be followed in Part 2 of the study through Post-Treatment Week 24 to assess  $SVR_{12}$  and  $SVR_{24}$ .

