### **8.1.2.1 Primary Efficacy Endpoint Across Parts 1 and 2**

The primary efficacy endpoint is the percentage of subjects with SVR12 among all subjects. The 95% confidence interval for the SVR rate will be calculated.

To evaluate the hypothesis that the percentage of HCV pediatric subjects treated with ombitasvir/paritaprevir/r, with or without dasabuvir with or without RBV who achieve SVR12 is superior to the historical SVR rate for the pediatric population treated with pegIFN and RBV, the lower bound of the 2-sided 95% CI of the percentage of subjects with SVR12 must be greater than 67% (Section 5.6.3).

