## **8.2 Determination of Sample Size**

The sample size of 36 subjects in Part 1 will adequately characterize the pharmacokinetics of the AbbVie DAAs to enable dose selection in pediatric subjects.

According to the Prescribing Information of PEGASYS, the SVR24 rate was 47% among 45 treatment-naïve pediatric subjects with HCV GT1 in the NV17424 trial. To show that

the DAA regimen is superior to this current standard of care by 20% in Parts 1 and 2, the lower bound of the 2-sided 95% confidence interval of the SVR12 rate across all subjects in the study must be greater than 67%. For the primary efficacy endpoint of the percentage of subjects with SVR12, if it is assumed 90% subjects would achieve SVR12 then 50 or more subjects would have > 90% power to have a lower bound of 2-sided confidence interval based on normal approximation to the binomial distribution > 67%.

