#### **4.4                   Planned Analysis**

An interim analysis will occur after all subjects in Part 1 or Part 2 have completed the PT Week 12 Visit or prematurely discontinued from study. The database will be versioned after performing appropriate data cleaning. Final data through PT Week 144 will be locked in a later version of the database. SAS® (SAS Institute, Inc., Cary, NC) for the UNIX operating system will be used for all analyses. All statistical tests and all confidence intervals will be two-sided with an  $\alpha$  level of 0.05.

All analyses will be conducted by statisticians and statistical programmers at AbbVie or their designees according to the methodologies specified in this SAP.

There is no intention of changing the study design based on efficacy findings from the PT Week 12 interim analysis. The intention is to follow all subjects who receive study drug for at least 144 weeks following treatment. There will be no statistical adjustment employed due to this interim analysis.

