### **10.3.2 Primary Efficacy Analysis Across Parts 1 and 2.**

The primary efficacy endpoint across Parts 1 and 2 is:

- The percentage of subjects with  $SVR_{12}$  among all subjects.

The  $SVR_{12}$  rate and corresponding 2-sided 95% confidence interval will be presented.

For both the primary and secondary efficacy endpoints, the Wilson's score method will be used to calculate the confidence interval.

According to the Highlights of Prescribing Information of PEGASYS®, the  $SVR_{24}$  rate was 47% among 45 treatment-naïve pediatric subjects with HCV GT1 in the NV17424 trial. To show that the DAA regimen is superior to this current standard of care by 20%, the lower bound of the 2-sided 95% confidence interval of the  $SVR_{12}$  rate across all subjects in the study must be greater than 67%.

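### The 67% hurdle describes GT1 treatment-naïve children, both comparisons with it pool GT4 and interferon-experienced subjects, and no planned analysis sets the matching group against it

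*Protocol*

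**What the plan says.** Protocol 5.6.3 takes its benchmark from the peginterferon label, where the SVR24 "rate was 47% among 45 treatment-naïve pediatric subjects with HCV GT1 in the NV17424 trial". Protocol 8.2 and SAP 4.3 and 10.3.2 repeat the figure. Adding 20 points gives 67%.

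The test covers everyone treated. In Protocol 5.6.3 the lower 95% bound for SVR12 "across all subjects in the study must be greater than 67" per cent, and SAP 10.3.2 requires that the "rate across all subjects in the study must be greater than 67" per cent. The hypothesis in Protocol 8.1.2.1 is worded more widely than the benchmark: the regimen "is superior to the historical SVR rate for the pediatric population treated with pegIFN and RBV". Protocol 8.1.2.2 and SAP 10.4 also compare SVR24 with 67% across all subjects, and SAP 10.2 places that comparison after SVR12.

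Part 1 plans about 36 GT1 treatment-naïve subjects. Protocol 5.1 then says "Part 2 will enroll approximately 16 HCV GT1-infected and 10 GT4-infected, treatment-naïve or IFN"-experienced. Protocol 5.5.3 caps Part 2 enrolment by genotype only, without regard to prior treatment.

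SAP 10.5 summarises SVR12 by genotype and, separately, by prior treatment, with Wilson intervals where a subgroup has at least 10 subjects. These summaries are not crossed and are not set against 67%. The two sensitivity populations (SAP 5.1.1 and 10.6) keep GT4 and experienced subjects.

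**The concern.** In a single-arm study, a statement of superiority over a historical rate depends on the historical and tested groups being alike. Here they differ in genotype and in treatment history. Neither document gives a peginterferon/ribavirin rate for GT4 or interferon-experienced children, or a reason why 47% should stand for them.

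A pooled lower bound above 67% therefore shows that the mixed population exceeds 67%. It does not show that the group behind the 47% does so. If the two results differed, the planned tables would not reveal it directly, because GT1 treatment-naïve subjects are never defined as an analysis set.

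**Working it through.** **Inputs.** Hurdle 67%; two-sided 95% interval (SAP 4.4: "All statistical tests and all confidence intervals will be two-sided"); Wilson method (SAP 10.3.2); planning rate 90% (Protocol 8.2: "if it is assumed 90% subjects would achieve" SVR12); total about 62, made up of 36 GT1-naïve in Part 1 plus 16 GT1 and 10 GT4 in Part 2. The number outside the benchmark runs from 10 (GT4 only, all GT1 naïve) to 26 (every Part 2 subject GT4 or experienced).

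**Formulas.** With p = x/n and z = 1.96, the Wilson lower bound is

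L = [p + z²/(2n) − z√(p(1−p)/n + z²/(4n²))] / (1 + z²/n).

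The pass count r is the smallest x with L > 0.67. Power is P(X ≥ r), X ~ Bin(n, 0.90).

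**The plan's own figure.** Protocol 8.2 says "50 or more subjects would have > 90% power" under the normal approximation. At n = 50 that method gives r = 40 (lower bound 68.9%) and exact power 99.1%. Wilson gives r = 41 (69.2%) and 97.5%. The stated figure holds either way.

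**Pooled rule at n = 62.** For x = 49, p = 0.7903 and L = (0.7903 + 0.0310 − 0.1060)/1.0620 = 67.4%, a pass. For x = 48, L = 65.6%, a fail. So r = 49, with power 99.7% if everyone's true rate is 90%. The protocol's normal approximation would pass at 48 (67.01%), one responder fewer, which does not change the argument.

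**Stress case: all non-benchmark subjects respond.**

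| Mix (GT1-naïve + others) | GT1-naïve responders at a pooled pass | Own lower bound | Needed alone |
|---|---|---|---|
| 52 + 10 | 49 − 10 = 39/52 (75.0%) | 61.8% | 42/52 (80.8%) |
| 36 + 26 | 49 − 26 = 23/36 (63.9%) | 47.6% | 30/36 (83.3%) |

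**How likely is disagreement?** Let B be GT1-naïve responders and K the others. The chance that the pooled test passes while the matched group misses its own bound is P(B + K ≥ 49 and B < r_B), where r_B is 42 or 30. With a true GT1-naïve rate of 90%:

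- 52 + 10, with GT4 at 100% (the adult rate with ribavirin in Protocol 3.2): 1.2%.
- 36 + 26, with the others at 95% (assumed): 6.3%.

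At a GT1-naïve rate of 95% these fall to below 0.01% and 0.2%.

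**The other direction.** With GT1-naïve at 90% and 26 others at 70% (assumed), the pooled test passes 77% of the time. The 36 matched subjects alone would pass 93.7% of the time.

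**The matched analysis on its own.** At n = 36, 30/36 has lower bound 68.1%, one-sided type I error 2.4% and power 93.7% at 90%. At n = 52, 42/52 has lower bound 68.1% and power 98.7%.

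**The case against.** The strongest reply is that the plan is consistent. Every statement of the primary endpoint says all subjects, and Protocol 5.6.4 describes the mixed population as agreed in the paediatric plans. Protocol 3.0 also gives high adult rates for these groups: 96–97% in non-cirrhotic GT1a, 100% in GT1b without ribavirin, 100% in non-cirrhotic GT4 with ribavirin and 97% in cirrhotic GT4 at 12 weeks. A gap of about 30 points between GT1 and GT4 has no support there. This stands, and it is why the table above is a stress case and not a forecast.

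A reader might infer that pooling inflates the type I error. If GT1 were truly at 67% and GT4 at 100%, the pooled rule would pass 13.9% of the time in the 52 + 10 mix, against 2.1% for GT1 alone. But the all-subject rate would then be (0.67 × 52 + 10)/62 = 72.3%. The plan's hypothesis would be true, and 13.9% would be power. It counts as error only if a GT1-naïve target replaces the plan's own.

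A reader might also infer that the non-benchmark subjects could carry the test alone, or that their number is open-ended. They are at most about 26, and a pass needs 49.

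The plan covers part of the gap. Genotype and prior treatment are summarised one at a time, and the mini-tablet stratum (about 24 subjects, Part 1 only) is entirely GT1 treatment-naïve. A reader could place those bounds beside 67%. The crossed set, and a stated comparison for it, are still missing.

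**Conclusion.** The mismatch is real and affects both comparisons with 67%. Its expected effect is small: about 1% to 6% chance of a pooled pass with a matched-group miss, assuming 90% in GT1-naïve subjects, 95% to 100% in the others and the enrolment mixes shown. The direction is not fixed, since poorer response in Part 2 would make pooling conservative.

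The documents do not support the stronger conclusion that the primary test is invalid or that the confirmatory claim must move to the GT1-naïve set. The pooled test answers the question the plan poses. What it lacks is a pre-specified result in the group the benchmark describes, together with wording that limits the comparison to that group. This is a cheap improvement, not a defect that undermines the trial.

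**What to change.** Keep pooled SVR12 as the primary test and leave the SAP 10.2 sequence unchanged. Add to SAP 10.6 a supportive analysis of SVR12 with a Wilson 95% interval in GT1 treatment-naïve subjects, meaning all of Part 1 plus treatment-naïve GT1 subjects in Part 2, and set the lower bound against 67%. Report it beside the primary result. State that the peginterferon/ribavirin benchmark describes GT1 treatment-naïve children, and that the superiority statement will be qualified if the two results disagree.

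The cost is one SAP paragraph, one table and a wider interval than the pooled one. No extra enrolment or data are needed, and power stays above the plan's 90% even if only the 36 Part 1 subjects qualify.
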